The purpose of this pilot study is to examine the acceptability and proof of concept effectiveness of a wireless, transcranial direct current stimulation for people with cognitive impairments. Sample size (n=10) is convenient and designed to explore acceptability and feasibility. Participants who are enrolled will be provided a tDCS device to use for a period of four weeks. They will have two study visits, baseline (BL) and the 4th week visit (V1). During each visit participants will answer various questionnaires to assess patient-reported outcomes such as sleep quality, cognitive impairment, depression, anxiety, fatigue, and user acceptability.

Section E: Protocol Risks/Subjects

E1. Risk Category

Category 1: Research not involving greater than minimum risk.

E2. Subjects

Gender:

Both

Age:

Adult (18-64 yrs), Geriatric (65+ yrs)

Ethnicity:

All Ethnicities

Primary Language:

English, Spanish

Groups to be recruited will include:

Both patients and healthy, non-patient, normals

Which if any of the following vulnerable populations will be recruited as subjects?

Vulnerable populations require special protections. How will you obtain informed consent, protect subject confidentiality, and prevent undue coercion?

E3. Pregnant woman/fetus

Will pregnant women and/or fetuses (as described in 45 CFR 46 Subpart B) be enrolled in the research?

No

E4. Neonates

Will neonates of uncertain viability or nonviable neonates (as described in 45 CFR 46 Subpart B) be enrolled in the research?

No

E5. Children

Will children be enrolled in the research?

No

Section F: Design/Procedure

F1. Design

Select one category that most adequately describes your research:

c) Pilot

Discuss the research design including but not limited to such issues as: probability of group assignment, potential for subject to be randomized to placebo group, use of control subjects, etc.

We will prospectively recruit 10 subjects with cognitive issues such as poor working memory, brain fog, or impairments due to dementia, Alzheimer's, or concussions. This will be a single-arm study, providing all recruited subjects with the tDCS treatment. All subjects will be followed and monitored for up to 4-weeks.

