At the baseline visit (BL) patients will receive the tDCS device (LIFTiD Neurostimulation, RPW Technology, LLC, NY, USA) and research staff will provide instruction on how to use the device along with a user manual. Patients will be asked to use the stimulation device for at maximum 20 minutes per day, for a period of 4-weeks. Finally, at the BL visit patients will also be asked to answer a number of questionnaires to assess patient-reported outcomes and cognition. These include: instrumental activity of daily living scale (IADL), daily living independence (KATZ), depression (CES-D), fatigue (FACIT), cognitive assessment (MOCA), attention(Number Span forward) working memory (Number Span backward), processing speed and executive functioning (Trail Making Test Part A and Part B), and memory encoding, recall, and recognition (Hopkins Verbal Learning Test), pain and mobility, global health (PROMIS), sleep (PSQI), frailty (TSFI, FRIED FRAILTY), anxiety (BAI), multi-dimensional assessment of fatigue (MAF), community engagement (Life-Space), and user acceptability (TAM).

At the final visit (V1), patients will return to the clinic and return the neurostimulation device. To assess feasibility and acceptability (Aim 1), patients will answer a technology acceptance model (TAM) questionnaire. This questionnaire will assess their perceived ease of use, perceived benefit and technology anxiety. Furthermore, patients will answer the same questionnaires assessed at baseline in order to address Aim 2. Both aims are listed below: - Aim 1: To examine feasibility and acceptability of tDCS in patients with cognitive issues.

- Aim 2: To examine effectiveness of tDCS in patients with cognitive issues.

Device: LIFTiD neurostimulation uses transcranial direct current stimulation (tDCS) technology and was developed to help improve the brain's potential through electrical stimulation. Patients will be given the LIFTiD device headband, 1 mirror, 1 plastic spoon, 6 white sponges, 1 USB cable and 1 plastic bottle in a packet at the BL visit.

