Preparation of device: 1. Patients must prepare a salt water solution in the plastic bottle provided using none iodized salt, tap water, and the provided measuring spoon. 2. Two sponges should be dampened with tap water and then saturated with the salt water solution made in step 1 on both sides. 3. Sponges should be placed in the electrodes in the LIFTiD headband. 4. LIFTiD headband should be placed on the forehead, centered and straight across. 5. Once fit, patient should

use the on/off button to begin stimulation. 6. Device automatically powers down after 20 minutes.

Stimulation frequency: maximum of 20 minutes daily. During the Stimulation the patient should perform an activity, such as read, answer emails, homework, etc.

After the completion of the study the patient should return the LIFTID device to the Research Coordinator.

All in-person visits will occur at Baylor College of Medicine McNair Campus. Research staff may call patients in between the two visits to assess compliance and answer questions. Patients will not be paid for in person visits or phone calls.

Section G: Sample Size/Data Analysis

G1. Sample Size

How many subjects (or specimens, or charts) will be used in this study?

Local: 10 Worldwide: 10

Please indicate why you chose the sample size proposed:

Convenient and selected based on available resources to demonstrate feasibility and the proof of concept effectiveness of tDCS therapy. We plan to recruit 10 eligible subjects.

G2. Data Analysis

Provide a description of your plan for data analysis. State the types of comparisons you plan (e.g. comparison of means, comparison of proportions, regressions, analysis of variance). Which is the PRIMARY comparison/analysis? How will the analyses proposed relate to the primary purposes of your study?

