Independent t-test, U-test, or Chi-square (depends on type of variables) to compare between groups (AG, and PG for key baseline descriptors including demographics and relevant clinical characteristics. Those descriptors which show statistical significant difference, baseline value of the outcomes measured in the model, and other variables that are deemed to be prognostic, will be considered as covariates for adjusting the results in the following assessments. Appropriate mixed models (linear for continuous or Generalized Estimating Equations (GEEs) for non-continuous or non-parametric variables) will be used to test the intervention effect for each of the outcomes. Results will be adjusted by covariates as described above.

Section H: Potential Risks/Discomforts

H1. Potential Risks/Discomforts

Describe and assess any potential risks/discomforts; (physical, psychological, social, legal, or other) and assess the likelihood and seriousness of such risks:

The devices and technologies are completely non-invasive, safe, non-toxic and non-ionizing. The potential risks to subject are minimal. However, like any battery powered systems, there is a minimum risk of sensor malfunctioning. In addition, the study devices are not waterproof, and although they use a low powered battery (similar to a cellphone battery), in order to avoid any risk of shock the monitor should not be submerged or saturated with fluids during operations or cleaning. It does not emit any radiation to the human body, and does not offer any significant risk to the subject.

Subjects may experience mild discomfort or irritation from the band or sponges on their forehead and mild headaches during adaptation period after initiating therapy. We will inform the subject to please notify the investigators if the band or sponges are uncomfortable.

All information we will collect about the subject will be stored in a secure location and coded in a way to maintain confidentiality. Only study personnel will have access to their records. Data collected during the study may be published and made publicly available. Data may also be shared with other research groups. However, data that could in any way identify them will not be made public or shared.

H2. Data and safety monitoring plan

Do the study activities impart greater than minimal risk to subjects?

No

H3. Coordination of information among sites for multi-site research

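### G2 is written for two undefined groups (AG and PG) in a single-arm pilot, states no baseline-to-week-4 contrast, and names no primary analysis or exploratory status for its tests

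*Combined protocol and SAP*

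**What the plan says.** - **Design.** F1: "This will be a single-arm study, providing all recruited subjects with the tDCS treatment". There are two visits, BL and V1.
- **Baseline comparison.** G2 plans a t-test, U-test or chi-square "to compare between groups (AG, and PG for key baseline descriptors". AG and PG appear nowhere else in the document.
- **Covariates.** G2 lists three sources. It begins "Those descriptors which show statistical significant difference, baseline value of the outcomes measured in the model" and then adds other variables judged prognostic.
- **Outcome models.** Linear mixed models or GEEs "will be used to test the intervention effect for each of the outcomes". The sentence names neither groups nor visits.
- **Primary analysis.** The G2 prompt asks: "Which is the PRIMARY comparison/analysis? How will the analyses proposed relate to the primary purposes of your study". The answer names no primary outcome or analysis. It refers to statistical significance without giving a level.
- **Purpose.** Section D: "Sample size (n=10) is convenient and designed to explore acceptability and feasibility". G1 says the sample was selected "to demonstrate feasibility and the proof of concept effectiveness of tDCS therapy". F2 gives "Aim 2: To examine effectiveness of tDCS in patients with cognitive issues" and has the baseline questionnaires repeated at V1 to address it.
- **Outcomes.** F1 and F2 each list a battery, and the F2 list is longer. F2 assigns the technology acceptance questionnaire (TAM) to Aim 1.

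**The concern.** The analysis section does not match the design it serves. Part of it needs a second group that will not exist. The part that could still be used does not say what is compared with what. The Aim 2 analysis would therefore have to be settled later, possibly with the data in view.

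The missing primary analysis adds to this. Many scores are tested, none has priority, and G2 attaches no exploratory label. The documents set no rule for what would count as proof of concept, so a reader of the results could not tell a planned finding from a selected one. Unadjusted testing is acceptable in a 10-person pilot when it is labelled exploratory. The gap is that G2 does not do so.

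**Working it through.** **1. The plan's own figure.** The only design figure is n = 10, described as convenient. No alpha, power, effect size or SD lies behind it, so there is nothing to reproduce.

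**2. G2 set against the design.**

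| G2 element | Needs two groups? | Can it be run with one arm? |
|---|---|---|
| Baseline tests, AG versus PG | Yes | No |
| Covariates from significant between-group differences | Yes | No |
| Baseline value of the outcome as covariate | No | Yes, but its role is unclear (step 3) |
| Other prognostic variables as covariates | No | Yes |
| Mixed model or GEE for each outcome | Not stated | Yes, if a visit term is added |

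**3. What the intervention effect could mean.** If BL and V1 are both outcome rows, the visit coefficient is the mean change. The baseline value is then already part of the response, and G2 also lists it as a covariate. If only V1 is the outcome and BL is an adjuster, each subject has one row. There is then no repeated measure to model, and with no comparator the intercept is the expected V1 score at a baseline of zero, which is not an effect of treatment. G2 does not say which is meant.

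**4. Counting the scores, without TAM.**
- F1 list: IADL, KATZ, CES-D, FACIT, MOCA, pain and mobility, PROMIS, PSQI, TSFI, Fried, BAI, MAF, Life-Space = 13.
- F2 list: those 13, plus Number Span forward and backward, Trail Making A and B, and Hopkins = 13 + 5 = 18. Counting Hopkins encoding, recall and recognition separately gives 18 + 2 = 20.

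These counts are a reading of the lists and are not stated in the documents. Combining or splitting the pain, mobility and PROMIS entries moves the F2 count by one or two.

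**5. Scale, under assumptions the documents do not state.** Assume two-sided 5% paired t-tests on normal change scores, n = 10, no true change, and any one favourable score read as success. Each test has a 2.5% chance of a false improvement. For K independent scores, P(at least one) = 1 − 0.975^K:
- K = 13: 1 − 0.975^13 = 0.280
- K = 18: 1 − 0.975^18 = 0.366
- K = 20: 1 − 0.975^20 = 0.397

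Several scales overlap, so independence is unlikely. Simulation with a common correlation (200,000 replicates) gives:

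| Correlation | K = 13 | K = 18 | K = 20 |
|---|---|---|---|
| 0.3 | 0.223 | 0.276 | 0.295 |
| 0.5 | 0.181 | 0.217 | 0.230 |
| 0.7 | 0.131 | 0.153 | 0.161 |
| 0.9 | 0.076 | 0.084 | 0.087 |

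**6. Precision at n = 10.** The 95% CI half-width for a mean change is t(0.975, 9 df)/√10 = 2.262/3.162 = 0.715 SD of the change.

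**The case against.** The strongest reply is that this is a pilot and says so. Sections D and G1 both attach proof of concept to effectiveness, the word Aim 2 uses. A reader might infer from G2 that the investigators plan confirmatory claims, but the documents do not support that. What remains is narrower: G2 itself does not label the tests exploratory.

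A reader might also infer that no test of the intervention can be run at all. That goes too far. Only the baseline comparison and one of the three covariate sources expressly need two groups. The model sentence names none, and with BL and V1 fixed, a visit term is an available reading. The objection succeeds here, but the contrast is still unstated.

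A third inference would be that the plan carries a false-positive rate near 40%. The documents contain no rule under which one favourable score counts as success, and G2 names mixed models and GEEs, not paired t-tests. The per-test rate depends on that choice. An uncorrected sandwich z-test at n = 10 gives about 4.8% false improvement per test instead of 2.5%. The rates in the working illustrate scale and do not describe the plan.

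Finally, section E2 ticks both patients and healthy subjects, which might seem to supply two groups. F1 recruits 10 subjects, all with cognitive issues, and gives all of them tDCS, so that entry does not explain AG and PG.

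**Conclusion.** The concern holds, and the two-group text is its main part. The AG/PG comparison and the covariate rule built on it cannot be run in the stated design. The outcome models can be run only after a contrast is supplied that G2 does not give. These conclusions rest on the text alone.

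The missing primary analysis and exploratory label are real but secondary. Absence of multiplicity adjustment is not a defect in its own right in a pilot of 10. Under the stated assumptions, the chance of at least one false improvement among 18 to 20 scores runs from about 37–40% (independent) to 8–9% (correlation 0.9). The range is wide because neither the correlation nor the decision rule is known.

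The matter should be corrected before analysis. It affects Aim 2. The Aim 1 questions on feasibility and acceptability do not depend on it.

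**What to change.** Before analysis:

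1. Delete the AG/PG comparison and the between-group covariate selection. Specify within-subject change from BL to V1 with a 95% CI for each outcome.
2. Do one of the following; either is adequate here.
   - Name one Aim 2 primary outcome, chosen and justified by the investigators, with a stated alpha, and label the other outcomes exploratory.
   - Label all Aim 2 outcomes exploratory, report estimates with CIs, and make no significance or effectiveness claim.
3. State that uncontrolled pre-post change cannot separate a device effect from practice effects or regression to the mean. Naming one primary outcome does not remove this limit.
4. Reconcile the outcome lists in F1 and F2 so that the analysed set is fixed.

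The cost is wording only, with no added visits, tests or participants. The investigators give up significance claims on the non-primary scores, or on all Aim 2 scores under the second choice. Estimates will be imprecise either way, at about ±0.72 SD of the change.

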Is the BCM Principal Investigator acting as the SPONSOR-INVESTIGATOR for this multi-site research?

No or Not Applicable

Is BCM the COORDINATING CENTER for this multi-site research?

No or Not Applicable

Section I: Potential Benefits

Describe potential benefit(s) to be gained by the individual subject as a result of participating in the planned work.

There is potential benefit of improvement of memory or cognitive functioning based on previous study of the use of tDCS.
The patients might find it easier to concentrate or focus on a task.

Describe potential benefit(s) to society of the planned work.

As described above, this type of work may allow physicians to provide more personalized care for patients with cognitive impairments.

Do anticipated benefits outweigh potential risks? Discuss the risk-to-benefit ratio.

This study brings no more than minimal risk to subjects as it only involves a non-invasive device. There are some risks associated with lack of comfort from tDCS, , risk associated with electrical malfunction of the tDCS device, and other unknown risks. All devices will be checked before any use to minimize the risk associated with electrical malfunction. Although there is no direct benefit for participating in the study, their participation may help the investigators better understand the impact and functionality of tDCS.

Section J: Consent Procedures

J1. Waiver of Consent

Will any portion of this research require a waiver of consent and authorization?

No

J1a. Waiver of requirement for written documentation of Consent

Will this research require a waiver of the requirement for written documentation of informed consent?

No

J2. Consent Procedures

Who will recruit subjects for this study?

PI
PI's staff

Describe how research population will be identified, recruitment procedures, any waiting period between informing the prospective participant and obtaining consent, steps taken to minimize the possibility of coercion or undue influence and consent procedures in detail.

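### The visible plan learns of adverse effects only if subjects volunteer band or sponge discomfort, so effects it names elsewhere are likely to be under-counted

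*Combined protocol and SAP*

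**What the plan says.** **Reporting route.** H1 says: "We will inform the subject to please notify the investigators if the band or sponges are uncomfortable". The subject must start the report, and its subject matter is comfort of the band or sponges.

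**Risks named.** The sentence before it in H1 expects mild irritation or discomfort where the band and sponges sit, and also mild headache early in use. Section I adds "risk associated with electrical malfunction of the tDCS device, and other unknown risks".

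**Contacts.** Section D sets two visits, baseline and week 4 (V1). On contact between them, F2 says: "Research staff may call patients in between the two visits to assess compliance and answer questions".

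**Instruments at V1.** F2 assigns Aim 1 (feasibility and acceptability) to the technology acceptance questionnaire, which covers how easy the device is to use, its perceived benefit and unease with technology. The baseline questionnaires, including pain, sleep, anxiety and fatigue, are repeated for Aim 2.

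**Design.** F1 says: "This will be a single-arm study, providing all recruited subjects with the tDCS treatment". G1 says: "We plan to recruit 10 eligible subjects".

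**Safety monitoring and analysis.** H2 answers that risk is not greater than minimal, and no monitoring plan follows. G2 contains no summary of adverse effects.

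**The concern.** The plan names several possible harms but describes asking about only one kind, and leaves even that to the subject to raise. An unknown risk cannot be found by inviting comments on sponge comfort.

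The method fits the population poorly. F1 enrols adults with poor working memory, brain fog or cognitive impairment, including dementia. F2 has them prepare the saline and sponges themselves, and describes no supervised sessions. A brief headache in the first week has to be noticed, remembered and volunteered, possibly weeks later.

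At stake is how the pilot will be read. If few or no effects are recorded, a reader cannot tell a well-tolerated device from a method that did not ask. Acceptability findings under Aim 1 would be read alongside that low count and would look better than they should.

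**Working it through.** **Step 1. Is there a figure in the plan to reproduce?** No. Section D states: "Sample size (n=10) is convenient and designed to explore acceptability and feasibility". The documents give no event rate, no reporting fraction and no safety target.

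**Step 2. Set each named risk against each described means of learning about it.**

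| Risk named | H1 request | V1 instruments | Optional calls |
|---|---|---|---|
| Band or sponge discomfort or irritation (H1) | Covered, if volunteered | Not described as asked | Not described as asked |
| Mild headache (H1) | Not covered | Not described as asked | Not described as asked |
| Electrical malfunction (Section I) | Not covered | Not described as asked | Not described as asked |
| Unknown risks (Section I) | Not covered | Not described as asked | Not described as asked |

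The repeated pain, sleep, anxiety and fatigue scales do elicit symptoms, but as Aim 2 outcomes. With no control arm, a change in score cannot be attributed to the device.

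**Step 3. Illustrate what incomplete capture does with 10 subjects.** Let p be the true proportion of subjects with an effect and d the share of affected subjects whose effect is recorded. Both are assumptions. Subjects are taken as independent, so each is recorded as affected with probability p × d.

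*Upper bound when no subject is recorded.* The one-sided 95% exact bound on p × d is 1 − 0.05^(1/10) = 0.259. Dividing by d gives the bound on p:

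- d = 1: 25.9%
- d = 0.75: 0.259 / 0.75 = 34.5%
- d = 0.5: 0.259 / 0.5 = 51.8%
- d = 0.25: 0.259 / 0.25 exceeds 1, so 0/10 sets no limit

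*Chance that no affected subject is recorded*, (1 − p × d)^10:

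| True rate p (assumed) | d = 1 | d = 0.75 | d = 0.5 | d = 0.25 |
|---|---|---|---|---|
| 10% | 0.349 | 0.459 | 0.599 | 0.776 |
| 20% | 0.107 | 0.197 | 0.349 | 0.599 |
| 30% | 0.028 | 0.078 | 0.197 | 0.459 |

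At p = 20%, for example, the chance of recording at least one affected subject is 1 − 0.107 = 89% with full capture, 1 − 0.349 = 65% at d = 0.5 and 1 − 0.599 = 40% at d = 0.25.

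*Expected number recorded*, 10 × p × d: at p = 30% this is 3.0 with full capture, 1.5 at d = 0.5 and 0.75 at d = 0.25.

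The direction follows whenever d is below 1. The size depends wholly on the assumed d and p.

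**The case against.** **The silence may not be real.** H1 is an ethics-form field about risks, not a data-collection section. Reporting instructions often sit in the consent form, device attachment or user manual, none of which was seen. This stands: the point is about the visible text only.

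**No tolerability result is planned.** Aim 1 is feasibility and acceptability, and G2 plans no event count. A reader might infer that a planned tolerability estimate will be biased. The documents do not support that, because there is no such estimate. What is exposed is any informal statement about tolerability and the interpretation of Aim 1.

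**Under-counting is not certain.** A reader might infer that effects will definitely be missed, or that skin irritation is ignored. Neither follows. No reporting fraction is given, and the H1 request does reach irritation from the band or sponges. F1 excludes severe cognitive decline that limits device use, and J6 excludes adults without capacity to consent. Eligibility extends to brain fog and concussion, so not every subject will have marked memory loss. Home use is a reasonable inference from F2 but is not stated.

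**Other contact exists.** Every subject attends V1, calls are possible, and F1 says: "All subjects will be followed and monitored for up to 4-weeks". These give opportunities to ask, but the plan does not say that adverse effects are asked about at any of them, nor what the monitoring consists of.

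**The study is small and minimal-risk.** Even with full capture, 0/10 allows a true rate up to 26%, and a checklist does not change that. This stands as a limit on what the pilot can show. It is not a reason to leave ten subjects unasked about effects the protocol itself anticipates.

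**Conclusion.** The concern holds in a limited form. In the visible text, adverse effects come to light only if a subject volunteers band or sponge discomfort. Headache, malfunction and unknown risks are named but are not described as being asked about. Given the population and the four weeks between visits, volunteered reports are likely to under-count effects, which would make a statement of good tolerability, and the reading of Aim 1, too favourable.

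The size cannot be derived from the documents. If capture were between 50% and 100%, the upper bound attached to 0/10 would lie between 52% and 26%. That range is illustrative, and it rests on the assumed capture and on independence between subjects. No stated aim or analysis is invalidated. The conclusion would weaken if the consent or device pages already provide for structured questioning.

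**What to change.** Keep the notification request and add a short fixed checklist, asked in the same words of every subject at V1 and at any call that is made. It should cover headache, skin irritation, pain or tingling, device malfunction, any other new symptom, the severity of each, and whether the subject stopped using the device.

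Add to G2 a descriptive summary: for each effect, the number of subjects affected out of all who received a device, with an exact 95% confidence interval. With 0/10 the two-sided interval would run from 0 to 1 − 0.025^(1/10) = 30.8%, which makes the limit of the sample plain. State which effects were solicited and which were volunteered. If the consent or device pages already contain such questions, cite them in F2 and H1.

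This is a cheap improvement: one page, no added visit and no change to treatment. The cost is a few minutes per contact and a likely higher reported event rate.
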